#### 5.3 RESTRICTIONS

In the event that defibrillation is required, disconnect the pump from the dressing prior to defibrillation. Remove the dressing if it is positioned in a location that will interfere with defibrillation.

Avance® Solo is not MRI compatible. Do not take Avance Solo into the MRI suite.

**Avance**® **Solo** has not been studied on paediatric patients. Patient size and weight should be considered when prescribing this therapy.

**Avance**® **Solo** is unsuitable for use in areas where there is a danger of explosion (e.g. hyperbaric oxygen unit).

**Avance® Solo** is not suitable for use in the presence of a flammable anaesthetic mixture or with oxygen or nitrous oxide.

The use of anticoagulants does not deem a patient inappropriate for treatment with **Avance® Solo**, however haemostasis must be achieved before applying the dressing and continued frequent assessment must be maintained and considered throughout the therapy.

At all times care should be taken to ensure that the pump and tubing does not:

- Lie in a position where it could cause pressure damage to the patient.
- Trail across the floor where it could present a trip hazard or become contaminated.
- Present a risk of strangulation or a tourniquet to patients.
- Rest on or pass over a source of heat.
- Become twisted or trapped under clothing or bandages so that the negative pressure is blocked.

#### 6 EVALUATION METHODOLOGY

#### 6.1 ASSESSMENT TIME-POINTS AND DATA RECORDED

Patients will have 2 Avance® Solo kits available (each with 2 dressings) and data will be captured on all dressing changes conducted with these 2 kits. No additional procedures will be carried out, outside of the patient's standard treatment. (for batteries are provided with each pump, additional battery should not be required). For the control arm up to 4 products per 14 day period will be provided.

# At baseline assessment the following parameters will be requested prior to application of dressings:

- Treatment setting (Operating room/hospital bed)
- Dressing routinely used (Foam, Film, non-woven, hydrocolloid, alginate, other)
- Patient demographics (Age, gender)
- Size of dressing used Type of surgery Date of surgery
- Location of surgical incision site (Left or right side, head/neck, chest, back, abdomen, retroperitoneal, groin, upper or lower arm, upper or lower leg, other)
- Risk factors for a surgical incision healing complication (obesity, smoker, low vascularity, diabetes, radiotherapy, immuno-compromised patient, or other)
- Length of incision (cm)
- Method of closure (Sutures, staples, tissue adhesive/glues, skin closure tape, other)
- Exudate level (None, slight, moderate, heavy)
- Drain present (yes/no)
- Condition of surrounding skin (Healthy, inflamed, macerated, dry and flaky, other)
- Assessment of infection (yes/no)
- Any incision complications and / or clinical signs of infection present (None, incision site static or deteriorating, dehiscence, increased exudate/secretion levels, increased pain, increased temperature around the wound, discolouration of granulation tissue, friable granulation, tissue necrosis, local erythema, oedema, purulent drainage, odour, other)

Photographs (yes/no)

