# 1.2 OBJECTIVE(S)

The primary objective is to assess the frequency of a wound healing complication, in a closed incisional wound in a "high risk" surgical incision when treated with NPWTi versus a highly absorbent antimicrobial post – operative absorbent dressing. (HAAMPOD).

A healing complication is defined as presence of at least one of the following conditions: infection (superficial or deep), dehiscence (partial, superficial, or deep), or delayed healing (incision not 100% closed within 7 days of the first surgical procedure), drainage form the wound after 96 hours post operatively.

The secondary objectives are to assess any changes in the following assessments of the surgical incision weekly over the treatment period:

- Surrounding skin condition
- Incision complications, infection or clinical signs of infection
  - to assess the number and type of these complications individually including other postsurgical complications: skin necrosis, cellulitis, abscess, suture abscess, seroma, periwound edema or hematoma occurring within 21, 42, and 90 days postoperatively
- Pain during dressing changes

Assessment of the following at dressing changes:

- Duration/wear time
- Ease of use; difficulty with sleep
- Damage to surrounding skin on removal
- · Assessment of re-epithelialization/closure
- Patient comfort during wear; ease of ambulation
- Conformability of dressing
- Exudate management
- Reasons for removal

To assess the overall comparison of Avance® Solo to the HAMMPOD.

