# At dressing removals the following information will be requested

- Dressing changed since last assessment (yes/no) (if yes how many times has the dressing been changed).
- Dressing in place (yes/no) obtain photograph
- Damage to surrounding skin (none, mild, moderate, severe)
- Level of damage to the reference wound on removal (none, slight, moderate, severe)
- Level of damage to the surrounding skin on removal (none, slight, moderate, severe)
- Condition of surrounding skin on removal (Healthy, fragile, inflamed, macerated, dry and flaky, other)
- Assess closure/ re epithelialisation of the incision
- Patient comfort during wear (Very comfortable, comfortable, acceptable, uncomfortable, very uncomfortable)
- Exudate level (None, slight, moderate, heavy)
- Assessment of infection (yes/no)
- Any incision complications and / or clinical signs of infection present (None, incision site static or deteriorating, dehiscence, increased exudate/secretion levels, increased pain, increased temperature around the wound, discolouration of granulation tissue, friable granulation, tissue necrosis, local erythema, oedema, purulent drainage, odour, other)
- Photographs (yes/no)
- Pain on removal of dressing (None, mild, moderate, severe)
- Reasons for removal (Dressing saturated, strike through, leakage, pain, Fell
  off, removed by patient, suture/staple removal, patients own request,
  inspection prior to patient discharge, other)
- Ease of use at this assessment (only at final removal)
- Occurrence of any product related adverse events will be documented at any point during the evaluation if required
- Is another dressing being applied at this assessment (yes / no?)

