# At end of evaluation

- Reason for discontinuation (end of evaluation, wound closed, treatment interrupted for more than 3 days, Wound progressed sufficiently to warrant a change in treatment, patient withdrawn)
- Reason for patient withdrawal (product related adverse event, lack of response, poor compliance, patients own request, other)
- Overall acceptability of Avance®Solo to clinicians for indicated use (yes/no)
- Whether the clinicians were sufficiently satisfied with the following properties of the product overall in terms of:
- Exudate management
- Conformability
- Number of dressing changes, strips, pumps, canisters and batteries used
- Barrier to infection
- Condition of surrounding skin
- General (Ease of use, Dressing retention, durability, patient comfort & convenience)

- Pain on application of dressing (0-10 SCALE)
- Pain on removal of dressing (0-10 SCALE)
- Overall performance of dressing (1-5)
- Freedom from re-admission
- The use of post operative antibiotics
- The duration of post operative antibiotics if used

Comparison of Avance®Solo with HAAMPOD, whether the clinicians were satisfied with Avance®Solo compared to HAAMPOD:

- Exudate management
- Conformability
- Number of dressing changes
- Barrier to infection
- Condition of surrounding skin
- General (Ease of use, Dressing retention, durability, patient comfort & convenience)
- Pain on application of dressing
- Pain on removal of dressing
- Overall performance of dressing
- Use of post operative oral antibiotics

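### Surrounding skin condition is to be assessed for change, but 'fragile' is a category at dressing removal and not at baseline, so skin that was already fragile can look like a new finding at the first removal

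*Combined protocol and SAP*

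**What the plan says.** Section 1.2 introduces the first group of secondary objectives with "The secondary objectives are to assess any changes in the following assessments of the surgical incision weekly over the treatment period". The first entry is "Surrounding skin condition", and pain at dressing changes is in the same group. Skin damage when a dressing is removed is in a separate group, of things assessed at dressing changes.

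Section 6.1 sets out what is recorded:

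- Skin condition at baseline, before any dressing is applied: "Condition of surrounding skin (Healthy, inflamed, macerated, dry and flaky, other".
- Skin condition at each removal: "Condition of surrounding skin on removal (Healthy, fragile, inflamed, macerated, dry and flaky, other".
- Skin damage at each removal, asked twice: "Damage to surrounding skin (none, mild, moderate, severe" and "Level of damage to the surrounding skin on removal (none, slight, moderate, severe".
- Pain at each removal: "Pain on removal of dressing (None, mild, moderate, severe". Pain on application is graded in the same four steps at each dressing change.
- Pain at the end of the evaluation: "Pain on removal of dressing (0-10 SCALE", with a matching 0-10 item for application.

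Section 8 specifies one analysis, a chi-squared test of the yes/no complication outcome, and describes the data as exploratory. It gives no definition of change for skin or pain.

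**The concern.** A change from baseline can be read only if the same state can be coded the same way on both occasions. For fragile skin it cannot. The population makes the gap relevant: Section 4.3.1 keeps patients on steroids or immunosuppressants eligible, and the baseline risk-factor list in Section 6.1 includes diabetes, low vascularity and radiotherapy. Section 3.1 also claims that the device's adhesive limits trauma to the surrounding skin, so readers will look at this outcome.

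The baseline state is recorded once. If it is not captured then, a patient whose skin was fragile all along may be indistinguishable on the form from one whose skin became fragile under the dressing.

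Two smaller ambiguities sit on the same forms. Surrounding-skin damage is asked twice with different wording for the second grade, and nothing says which answer is the outcome. Pain is collected on two scales, and nothing says which one serves the Section 1.2 objective. In an open-label study these choices are better made before data are seen.

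**Working it through.** There is no figure in the plan to reproduce: the Section 8 sample size does not depend on these items. The check is a comparison of the response lists in Section 6.1.

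| Item | Baseline | Each dressing change or removal | End of evaluation |
|---|---|---|---|
| Skin condition | 5 categories, including 'other' | the same 5 plus 'fragile' (6) | clinician satisfaction only |
| Skin damage | not asked | two four-grade items | not asked |
| Pain, application and removal | not asked | one four-grade scale | 0-10 |

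**Skin condition.** Removal list minus baseline list = {fragile}. Baseline list minus removal list = empty. So 6 - 5 = 1 category is unmatched.

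Consider a patient whose skin is fragile throughout:

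- Baseline to first removal: recorded as 'other' (or, say, 'healthy') and then 'fragile'. The record shows a change; the true state did not change.
- First to second removal: 'fragile' and then 'fragile'. The record is right, because all removals use one list.

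With identical lists, the first comparison would also read 'fragile' to 'fragile'. A patient whose skin was healthy and became fragile is recorded as 'healthy' to 'fragile', the same as a fragile patient coded 'healthy' at baseline. The current lists cannot separate these two.

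**Size.** Number of spurious changes per arm = n × p × c, where:

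- n = 30 patients per arm (Section 4.1);
- p = share with fragile skin at baseline (not in the documents; assumed 0.10 to 0.30);
- c = share of those coded 'fragile' at first removal (not in the documents; 1 is the maximum).

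With c = 1: 30 × 0.10 × 1 = 3, and 30 × 0.30 × 1 = 9. These are ceilings. Any c below 1 lowers them in proportion.

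**Arms.** Section 6.1 gives no separate skin lists for the two arms, and Section 8 says that patients are randomised. The mismatch therefore applies to both arms alike and creates no systematic difference on its own.

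**Skin damage.** The two grade sets differ only in {mild, slight}. The item has no baseline and is not in the change group of Section 1.2, so the defect is duplication without a rule for disagreement.

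**Pain.** The four grades are the same at every dressing change, so change between dressing changes can be computed. The plan gives no mapping to the 0-10 score and does not propose to combine the two.

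**The case against.** The strongest reply is that little is lost. The baseline list ends in 'other', so fragile skin can be recorded, though not under its own name. Photographs are planned at baseline and at dressing changes. The two damage items may be meant to differ: the first follows the question on whether the dressing is in place and does not mention removal, while the second does. The pain grades are consistent where Section 1.2 needs them. The data are exploratory, and the only specified test is on another outcome.

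Most of this stands, and it limits the point. It does not remove it. Moving from 'other' to 'fragile' still reads as a change, Section 6.1 describes no text field beside 'other', and no rule provides for recoding from photographs. Section 8 presents the study as a pilot to check assumptions before a larger trial, which is a good reason to settle the forms now.

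A reader might also infer more than the documents support:

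- *That fragile skin at baseline would be counted as harm from the dressing.* No counting rule or skin-change rate is defined anywhere.
- *That the 0-10 pain score depends on recall over two weeks.* Section 6.1 states neither the recall period nor the rater.
- *That the two pain scales invalidate the pain outcome.* Nobody plans to pool or compare them.

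**Conclusion.** The point holds in a limited form. The baseline and removal lists for surrounding skin condition differ by one category, and following the forms as written can turn unchanged fragile skin into an apparent change at the first removal. Comparisons between removals are sound.

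It would be going too far to say that the planned skin and pain changes are wrong as recorded, or that the comparison of the arms is biased. The fault reaches only baseline-to-removal comparisons involving 'fragile', and it falls on both arms. The figure of 3 to 9 of 30 per arm is a ceiling. It rests on an assumed prevalence, on every such patient being coded 'fragile' at first removal, and on any shift of category being read as change.

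The duplicated damage item and the unnamed pain scale are ambiguities to clear up in the same edit. This is a minor data-collection matter on exploratory secondary outcomes.

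**What to change.** In Section 6.1:

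1. Add 'fragile' to the baseline skin-condition list so that it matches the removal list. State that a category is reported as new only if it was absent at that patient's baseline. The categories have no natural order, so a rule based on 'worsening' would not be defined.
2. Merge the two surrounding-skin damage items into one with one set of grades, or state how they differ and which is the outcome.
3. Name the four-grade score taken at each dressing change as the outcome for pain at dressing changes. Report the end-of-evaluation 0-10 score separately, as an overall rating. Requiring a 0-10 score at every application instead is not advised: Section 4.3 has the first dressing placed as the operation ends, when the patient may not be able to give one.

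The cost is a form edit and a sentence or two of definition, best done before the forms are used. No visit is added. The primary outcome, sample size and main analysis do not change.

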# At all dressing change assessments the following information will be requested

- Conformability of dressing (yes/no)
- Treatment setting (Operating room, hospital bed, clinic, home, other)
- Size of dressing used
- Photographs (yes/no)
- Pain on application of dressing (None, mild, moderate, severe)
- Ease of use at this assessment

# At dressing removals the following information will be requested

- Dressing changed since last assessment (yes/no) (if yes how many times has the dressing been changed).
- Dressing in place (yes/no) obtain photograph
- Damage to surrounding skin (none, mild, moderate, severe)
- Level of damage to the reference wound on removal (none, slight, moderate, severe)
- Level of damage to the surrounding skin on removal (none, slight, moderate, severe)
- Condition of surrounding skin on removal (Healthy, fragile, inflamed, macerated, dry and flaky, other)
- Assess closure/ re epithelialisation of the incision
- Patient comfort during wear (Very comfortable, comfortable, acceptable, uncomfortable, very uncomfortable)
- Exudate level (None, slight, moderate, heavy)
- Assessment of infection (yes/no)
- Any incision complications and / or clinical signs of infection present (None, incision site static or deteriorating, dehiscence, increased exudate/secretion levels, increased pain, increased temperature around the wound, discolouration of granulation tissue, friable granulation, tissue necrosis, local erythema, oedema, purulent drainage, odour, other)
- Photographs (yes/no)
- Pain on removal of dressing (None, mild, moderate, severe)
- Reasons for removal (Dressing saturated, strike through, leakage, pain, Fell
  off, removed by patient, suture/staple removal, patients own request,
  inspection prior to patient discharge, other)
- Ease of use at this assessment (only at final removal)
- Occurrence of any product related adverse events will be documented at any point during the evaluation if required
- Is another dressing being applied at this assessment (yes / no?)

# At end of evaluation

- Reason for discontinuation (end of evaluation, wound closed, treatment interrupted for more than 3 days, Wound progressed sufficiently to warrant a change in treatment, patient withdrawn)
- Reason for patient withdrawal (product related adverse event, lack of response, poor compliance, patients own request, other)
- Overall acceptability of Avance®Solo to clinicians for indicated use (yes/no)
- Whether the clinicians were sufficiently satisfied with the following properties of the product overall in terms of:
- Exudate management
- Conformability
- Number of dressing changes, strips, pumps, canisters and batteries used
- Barrier to infection
- Condition of surrounding skin
- General (Ease of use, Dressing retention, durability, patient comfort & convenience)

- Pain on application of dressing (0-10 SCALE)
- Pain on removal of dressing (0-10 SCALE)
- Overall performance of dressing (1-5)
- Freedom from re-admission
- The use of post operative antibiotics
- The duration of post operative antibiotics if used

Comparison of Avance®Solo with HAAMPOD, whether the clinicians were satisfied with Avance®Solo compared to HAAMPOD:

- Exudate management
- Conformability
- Number of dressing changes
- Barrier to infection
- Condition of surrounding skin
- General (Ease of use, Dressing retention, durability, patient comfort & convenience)
- Pain on application of dressing
- Pain on removal of dressing
- Overall performance of dressing
- Use of post operative oral antibiotics

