#### 2 EVALUATION DESIGN

# 2.1 EVALUATION DESIGN

Open label, two armed, prospective, single center, quality equivalency assessment.

Immediate post operative application of Avance® Solo Negative pressure wound therapy on "high risk" closed surgical incisions. Versus the hospital best clinical practice dressing HAAMPOD. (Please note there is no prospective clinical data driven data, the hospital purchasing department develops and indicates the brand based upon cost).

The patient will be undergoing:

- Foot and ankle surgery
- Vascular groin incision, vascular axillary incisions
- Long leg vein harvest incision
- Closed forefoot and major amputation surgery
- Possibly: breast augmentation and reduction surgery

\*Note: The surgical indication is chosen based upon previously published data of high risk incisions. (It is beyond the scope of a protocol to educate the IRB in regards to the full definitions of high risk surgical inicisions)

Patients will participate in the study for 4 applications or up to 2 weeks treatment, whichever comes first. During this time clinicians will be asked to complete questions pertaining to the incision and to the performance and overall acceptability of Avance®Solo or the HAAMPOD.

Throughout the evaluation patients will be treated according to the product instructions for use for either product.

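### Acceptability is worded for Avance Solo only, and no between-arm analysis of the product ratings is specified for the overall-comparison objective

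*Combined protocol and SAP*

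**What the plan says.** Section 1.2 closes its objectives with: "To assess the overall comparison of Avance® Solo to the HAMMPOD". It attaches no endpoint, scale or analysis to that aim.

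Section 2.1 describes an open-label, two-arm, single-centre design. It says clinicians will answer "questions pertaining to the incision and to the performance and overall acceptability of Avance®Solo or the HAAMPOD".

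The end-of-evaluation list in section 6.1 contains three kinds of product item:

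- **Acceptability**, named for one product: "Overall acceptability of Avance®Solo to clinicians for indicated use (yes/no").
- **Ratings in general wording.** These open with "Whether the clinicians were sufficiently satisfied with the following properties of the product overall in terms of" and a list of properties. They go on to "Pain on removal of dressing (0-10 SCALE"), the matching score for application, "Overall performance of dressing (1-5"), readmission and antibiotic use.
- **A relative item**, headed as the comparison: "Comparison of Avance®Solo with HAAMPOD, whether the clinicians were satisfied with Avance®Solo compared to HAAMPOD". It covers ten attributes and gives no response scale.

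Section 4.3 allows one dressing on the reference incision at a time, and sections 5.1 and 8 assign patients to one product or the other by randomisation. Section 8 specifies a single analysis, a chi-squared test of wound complication (yes or no), and calls the data exploratory.

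**The concern.** Randomisation lets product ratings from the two arms be compared without selection between the groups. That requires the same question, about the product actually used, in both arms, and a statement that the answers will be compared.

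The acceptability item fails the first condition as worded. The property-satisfaction block is doubtful: it follows directly after the Avance Solo acceptability item, and one of its entries counts pumps, canisters and batteries, which the control dressing does not have. A site could reasonably take the block as applying to Avance Solo only. The second condition is not met for any rating.

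The item carrying the comparison label does not fill the gap. If it is answered per patient, the clinician has seen only one of the two products on that incision and must draw on other patients or on general experience. If it is answered once per clinician, it yields as many answers as there are clinicians, a number the protocol does not give, and it is not tied to the randomised patients. In either case the clinician is unmasked and Avance Solo is the subject of the question. Expectation is a live issue here. Section 1.1 records more than 15 years of wide use of this therapy by the investigator, and sections 1.1 and 2.1 describe the control as lacking supporting data and chosen on cost.

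At stake is whether the overall-comparison objective is answered by a randomised contrast or by an opinion.

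**Working it through.** No figure in the plan bears on this point. The sample-size calculation in section 8 concerns wound complications only. The check is therefore a comparison of sections, followed by the precision that the fix would give.

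**1. Acceptability.** Section 2.1 refers to "overall acceptability of Avance®Solo or the HAAMPOD". The section 6.1 list names Avance Solo alone. Section 4.1 plans 30 patients per arm. Taking section 6.1 literally, with one answer per patient, there are at most 30 answers for Avance Solo and 0 for control, so no difference can be estimated. Taking section 2.1 literally, there are up to 30 in each arm. The two sections must be reconciled.

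**2. Relative item against the ratings already listed.** Each of the ten attributes in the comparison list has a counterpart earlier in the same end-of-evaluation list:

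| Attribute in the comparison list | Counterpart earlier in the list |
|---|---|
| Exudate management, conformability, barrier to infection, surrounding skin, general handling (5) | Property-satisfaction items |
| Number of dressing changes (1) | Number used |
| Pain on application, pain on removal (2) | 0-10 scores |
| Overall performance (1) | 1-5 score |
| Oral antibiotic use (1) | Antibiotic use and duration |

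That accounts for 5 + 1 + 2 + 1 + 1 = 10. The relative item therefore covers nothing that could not be compared between arms, once the counterparts are asked in both.

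**3. Analysis.** Section 8 names one outcome (complication) and one test (chi-squared). It mentions no between-arm summary, difference or interval for pain, performance, satisfaction or acceptability.

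**4. Precision of the proposed comparison.** The inputs are n = 30 per arm (section 4.1) and two-sided 95% intervals by normal approximation. The SDs and proportions are assumptions, because the documents give none.

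For a mean difference, half-width = 1.96 × SD × √(2/30) = 0.506 × SD.

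- 1-5 performance: SD 0.8 gives 0.40 points; SD 1.2 gives 0.61 points.
- 0-10 pain: SD 2 gives 1.0 points; SD 3 gives 1.5 points.

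For a yes/no item with the same true proportion p in both arms, half-width = 1.96 × √(2p(1−p)/30).

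- p = 0.5 gives 1.96 × √(0.50/30) = 0.253, about 25 percentage points.
- p = 0.9 gives 1.96 × √(0.18/30) = 0.152, about 15 percentage points.

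These figures describe what the fix would deliver. They do not measure the size of the defect.

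**The case against.** The strongest reply is that the material for a randomised comparison is already there. The 1-5 performance score and the 0-10 pain scores name no product. The dressing-change and removal lists in section 6.1 record comfort, conformability, skin damage, exudate and pain without restriction to one arm. The questionnaires themselves are not in the documents (section 9.1.1 says the investigator team creates them), and section 2.1 signals that both products will be rated. On this view only a sentence of analysis is missing. That largely stands, and it is why the point is minor. It does not remove the conflict over acceptability, the Avance-specific entry in the satisfaction block, or the absence of a planned between-arm analysis.

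The relative item also need not be pure prior opinion. One centre runs both arms, so clinicians may form a view from treating trial patients on each product. That is fair, but the view would still be unmasked and would not be a contrast between randomised groups.

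A reader might go further in three ways that the documents do not support:

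- **That the trial makes no use of its randomisation.** The complication outcome is compared between the randomised groups in section 8.
- **That the relative item can only favour Avance Solo.** No response scale is given, and a clinician who was not satisfied would be answering against Avance Solo. The item is asymmetric in wording, which is a lesser fault.
- **That the objective depends wholly on the opinion item.** Section 1.2 ties the objective to no item. What can be said is that this is the only item labelled as the comparison.

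**Conclusion.** The point holds as a limited inconsistency and omission. Acceptability is worded for one arm in section 6.1 and for both in section 2.1. The satisfaction block is partly specific to Avance Solo. The only labelled comparison is an unmasked relative opinion, and no between-arm analysis of product ratings is specified for the overall-comparison objective.

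Its clearest consequence is for acceptability: up to 30 answers against none, if section 6.1 is followed literally and the item is completed once per patient. For the remaining ratings the data may well exist in both arms, and what is missing is the stated comparison. The primary outcome is unaffected. Because this is a secondary objective in a trial declared exploratory, it is a worthwhile improvement and not a threat to the study.

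**What to change.** 1. In the end-of-evaluation list, word acceptability and property satisfaction for the product the patient was assigned, with identical wording in both arms. Record pump, canister and battery counts separately, as Avance Solo usage data. Align section 2.1 and section 6.1.
2. Add to section 8 that the overall-comparison objective will be answered by comparing acceptability, property satisfaction, 1-5 performance and 0-10 pain between the randomised arms, as differences with 95% confidence intervals and without a claim of significance.
3. State who completes the items that compare Avance Solo with HAAMPOD, and how often. Report them only as descriptive clinician opinion.

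The cost is questionnaire wording, a sentence or two of analysis text, and the same short form completed by control-arm clinicians. No visits or patients are added. The fix does not remove expectation bias: the ratings are made open label, and the report should say so.
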